## **1.0 BACKGROUND AND SIGNIFICANCE**

Systemic lupus erythematosus (SLE) is a complex autoimmune disease characterised by involvement of multiple organs with a female to male ratio of 12:1 with the highest incidence reported in women of child bearing age (15-44 years). In general, advances in diagnosis and management have led to significant improvements in outcomes. However fatigue remains a challenging and prevalent issue for SLE patients.

## 1.1 Fatigue in lupus

SLE patients consider fatigue to be one of the most pervasive and disabling aspects of their disease. As many as 85% report significant levels of fatigue, a prevalence far in excess of that observed in the general population and most other chronic disorders. Moreover, its impact permeates all aspects of life as reflected by fatigue's strong association with impaired quality of life and work disability. Despite these profound consequences, there is a dearth of accepted therapies and in a meta-analysis of 32 studies in over 9,000 rheumatoid arthritis patients (who receive similar treatments to SLE and also suffer from significant fatigue) who received biological treatments found these medications, while effective for pain and disease activity, showed modest and mixed impacts on improving fatigue.

The etiology of fatigue is likely to be complex and existing evidence supports a multi-dimensional origin. While many SLE patients describe cognitive features of fatigue (e.g. difficulties in concentrating), even more complain of physical aspects (e.g. needing to rest more). Physical fatigue is commonly attributed to problems with the skeletal muscle (indeed physical fatigue and muscle fatigue are synonymous terms). In fact, by measuring voluntary muscle contraction, others have observed significantly reduced skeletal muscle strength in SLE patients compared to healthy controls – a difference which could be explained by pathological abnormalities within the muscles. In the past, muscle biopsy studies have identified microscopic abnormalities in the majority of patients, ranging from muscle fiber atrophy to lymphocytic vasculitis.

### **1.2 Acupressure**

Self-administered acupressure is one possible safe, self-management technique for which may be effective for improving fatigue as well as physical and psychosocial functioning in several chronic disease populations. Acupressure, a technique derived from acupuncture, is a component of Traditional Chinese Medicine (TCM) in which pressure is applied to specific acupoints on the body using a finger or small device, to treat disease. Our prior research demonstrated that acupressure, self-administered by women with breast cancer, significantly reduced clinically significant fatigue by approximately one-third in fatigued breast cancer survivors and was superior to standard therapies. Moreover these self-rated improvements were maintained up to one month after treatment was discontinued.

However, impact on other chronic disease populations with fatigue is unknown. To explore this intervention in SLE, we propose to conduct a pilot randomized clinical trial in 72 SLE patients with established fatigue, through the following aims.

# 2.0 SPECIFIC AIMS

- 1. To determine the feasibility of recruiting and conducting acupressure in fatigued persons with lupus
- To explore the effect of two distinct acupressure formulas (relaxing and stimulating) plus usual care versus sham acupressure plus usual care and usual care alone on severity and impact of chronic fatigue (as measured by the Brief Fatigue Inventory)
  - a. Hypothesis: Both relaxing and stimulating acupressure are superior to sham acupressure and usual care, but relaxing acupressure is superior to stimulating acupressure

- 3. Secondary: To explore the effect of two distinct acupressure formulas (relaxing and stimulating) plus usual care versus sham acupressure plus usual care and to usual care alone on quality of life, sleep and pain
  - a. Hypothesis: Both relaxing and stimulating acupressure are superior to sham acupressure and usual care, but relaxing acupressure is superior to stimulating acupressure

### **3.0 PRELIMINARY DATA**

#### 3.1 Study 1: Self-administered for Fatigue in Breast Cancer Survivors 

A total of 424 survivors of stages 0 to III breast cancer who had completed cancer treatments at least 12 months previously were screened, and 288 were randomized, with 270 receiving relaxing acupressure (n = 94), stimulating acupressure (n = 90), or usual care (n = 86). One woman withdrew owing to bruising at the acupoints. At week 6 (post-treatment), the percentages of participants who achieved normal fatigue levels (Brief Fatigue Inventory score <4) were 66.2% (49 of 74) in relaxing acupressure, 60.9% (42 of 70) in stimulating acupressure, and 31.3% (26 of 84) in usual care. At week 10, a total of 56.3% (40 of 71) in relaxing acupressure, 60.9% (42 of 69) in stimulating acupressure, and 30.1% (25 of 83) in usual care continued to have normal fatigue (see Figure 1). At neither time point were the 2 acupressure groups significantly different. Relaxing acupressure, but not stimulating acupressure, showed significant improvements in sleep quality compared with usual care at week 6, but not at week

Figure 1. Effect of Two Types of Acupressure on Fatigue (Grey area represents normal fatigue levels <4 on BFI) 10. Only relaxing acupressure significantly improved quality of life vs usual care at weeks 6 and 10.

Both acupressure arms significantly reduced persistent

fatigue compared with usual care, but only relaxing acupressure had significant effects on sleep quality and quality of life. Relaxing acupressure offers a possible low-cost option for managing symptoms.

# 3.2 Study 2: Acupressure Modulates Sleepiness in the Classroom 

We conducted a single-blind randomized crossover study to determine whether self-administered acupressure has a significant effect on sleepiness in a population of healthy student participants in a prolonged lecture situation. Our study utilized 2 active acupressure treatments with hypothesized opposing effects, a relaxation treatment and a stimulation treatment, in a crossover design in which all participants received both treatments on different days. The study population consisted of thirty-nine subjects enrolled at the University of Michigan School of Public Health course on clinical research design and statistical analysis.

*Methods:* Acupressure regimens promoting mental stimulation or relaxation were utilized in a crossover design with subjects randomized to either Sequence I (day 1 stimulation – day 2 relaxation – day 3 relaxation) or Sequence II (day 1 relaxation – day 2 stimulation – day 3 stimulation). Each regimen was taught to all study participants by 2 members of the class who were previously trained in acupressure. Each regimen

consisted of a 15-minute self-administered session of acupressure at either 5 stimulatory or 5 relaxation points (3 minutes each). The stimulatory point formula consisted of *Si Shen Chong* and bilateral – Large Intestine 4 (LI 4), Stomach 36 (St 36), Kidney 1 (K 1), and Urinary Bladder 10 (UB 10). All points were stimulated using either the thumb or forefingers to massage in both clockwise and counterclockwise directions. The primary outcome was the difference between afternoon and morning scores on the Stanford Sleepiness Scale (SSS) (afternoon score – morning score). The SSS was administered 2 hours prior to and 3 hours after each acupressure regimen. The 3 hour endpoint was chosen because this was the end of the class period where students were most likely to be fatigued. Data were analyzed using the PROC MIXED procedure of SAS (version 8.2). This model incorporated the fixed effects of sequence (I or II), period (day 1, 2, or 3), treatment (relaxation or stimulation), and other covariates, as well as the random effects of subject within sequence.

*Results:* A mixed model regression analysis using the change in SSS as the dependent variable was performed and the following variables were retained from the model: treatment (p=0.019), day (p=0.004), AM caffeine (p=0.083), hours of overnight sleep (p=0.042), and AM upsetting event (p=0.071). No significant carry over effects between days or treatments were detected. The least squares means for the stimulation and relaxation acupressure treatments were 0.570 and 1.127, respectively, with a significant difference in change in alertness scores between the 2 acupressure treatments. The mean difference between morning and afternoon SSS scores are presented by treatment, sequence, and day in Figure 2 above. Participants in the relaxation

acupressure group took more naps (p=0.048) during day 1. Stimulating acupressure yielded a 0.56-point greater difference in score on the SSS, corresponding to less fatigue, compared to the relaxing acupressure treatment (p = 0.019). Day of study (p = 0.004) and hours of overnight sleep (p = 0.042) also significantly affected the change in SSS scores. Incorporating participants' beliefs as to which treatment they received did not significantly alter the observed treatment effect.

### 4.0 METHODS

We propose to perform a randomized, single-blind parallel clinical trial. This will be parallel design with four arms (relaxing acupressure plus usual care, stimulating acupressure plus usual care, sham acupressure plus usual care and usual care alone) for persistent fatigue in SLE. The study will be approximately 12 weeks in duration: **Screening** (up to 30 days in duration) consists of a phone call evaluation for study eligibility; **Treatment** (active treatment phase; 6 weeks in duration) will consist of random assignment to self-administered acupressure regiment plus usual care or usual care only daily for 6 weeks (outcomes will include fatigue, sleep, QOL, pain); and **Post-treatment follow-up** (4 weeks in duration) to evaluate the persistence of effects following 4 weeks of no treatment. We will allow up to +/- 2 weeks difference for study visits and the interim phone call in order to accommodate schedules.

### 4.1 Participants and Recruitment

Patients will be recruited from multiple University of Michigan Rheumatology Clinics including the Brighton Health Center and the Taubman Clinics at the University of Michigan Hospital. Both General Rheumatology and Lupus Specialty Clinics will be available for recruitment. Participants in other studies who have granted permission to be contacted about other research protocols (eg, MILES program or the Michigan Lupus Cohort), will also be recruited. Lastly, we will recruit from the UMHealthResearch.org website and from the surrounding community through the use of fliers.

# 4.2 Eligibility Criteria.

# 4.2.1 Participant Characterization

Eligible participants will be patients with SLE, classified according to the 1997 American College of Rheumatology (ACR) criteria, attending General Rheumatology and Lupus Specialty Clinics at the University of Michigan. Participants will undergo a full clinical assessment including collection of core measures such as disease damage (SLAQ), disease activity (SELENA SLEDAI), organ involvement, disease duration, medication use, serological status and co-morbidities. Furthermore, information of factors which may be associated with the reporting of fatigue will be collected. Eligible participants that are not a part of the U of M health system will be determined by completing a connective tissue disease screening questionnaire (CSQ), if scoring positive on the CSQ these participants will be asked to complete a medical records release form. Once the study team receives the medical records they will conduct a medical record review to ensure the ACR criteria for SLE has been met. Additional eligibility criteria are listed in Table 2.0. During screening, identification of an untreated mood disorder or suicidal ideations will exclude the participant from the study. The study team will provide a list of resources for those with an untreated mood disorder and will follow study protocol for dealing with severe depression and suicidal ideations.

# Table 2.0 Eligibility Criteria

Inclusion Criteria		Exclusion Criteria		
✓ ✓ ✓	Women aged 18 years and older Report chronic (>3months) clinically relevant fatigue, defined as a score of ≥4 on the Brief Fatigue Inventory (BFI) Have inactive disease, defined as SELENA SLEDAI ≤ 4, AND/OR no addition or increase in dose of corticosteroids, immunosuppressive agents, or	* *	Pregnant or breast feeding Have a diagnosis of untreated mood disorder, e.g., bipolar or major depressive disorder Have an initiation, a cessation or change of treatment of any chronic medications, dietary supplements, behavioral therapy, physical therapy etc., or any planned change of medications, supplements or therapies during the study	
✓	antimalarial medications or hospitalization in the last 30 days Have no commonly recognized medical explanations for fatigue (a history of cancer in the previous 5 years –except for certain low risk cancer, unstable thyroid disease, moderate to severe chronic kidney disease, moderate to severe anemia)	×	Acupuncture or acupressure receipt in past year	
√ √	Baseline glucocorticoid dose equivalent of ≤10mg prednisone. No other planned intervention for fatigue other than current stable medication regimen			

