### 4.7 Study Visits

#### 4.7.1 Screening- Participant Interaction #0 (to determine eligibility)

A screening phone call will be made to evaluate participant interest and eligibility including, comorbidities and ability to maintain a stable lifestyle over the course of the study. Sociodemographic and participant contact information will be collected. Fatigue will be assessed using the Brief Fatigue Inventory (BFI) and baseline depression and lupus disease activity status with the Patient Health Questionnaire 9 (PHQ-9) and the Systemic Lupus Activity Questionnaire (SLAQ). If a potential participant is not a part of the U of M health system they will complete the Connective Tissue Screening Questionnaire (CSQ) and will be sent an Authorization for Release of Protected Health Information form to complete and give to their health care provider.

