# 4.8 Assessment Measures.

# 4.81. Disease Activity

Systemic Lupus Activity Questionnaire (SLAQ): is a self-administered tool developed for screening and epidemiologic studies; it is not intended for clinical management or in place of physical examination. The SLAQ is based on items from a physician-scored activity index (SLAM) that are suitable for self-report. It includes 24 symptoms questions and a single numerical rating scale asking the patient to rate their disease activity over the past three months, based on their most active day during that time. While the SLAQ correlates well with physician tools, as with any measure that does not include laboratory measures, it will not detect abnormalities in laboratory findings among asymptomatic patients.

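### Table 2.0 joins the two limbs of its inactive-disease definition with AND/OR, so it permits two different populations, and no scheduled visit names the SELENA SLEDAI score that one limb needs

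*Combined protocol and SAP*

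**What the plan says.** The inclusion column of Table 2.0 asks that candidates "Have inactive disease, defined as SELENA SLEDAI ≤ 4, AND/OR no addition or increase in dose of corticosteroids", then extends the drug list to immunosuppressives and "antimalarial medications or hospitalization in the last 30 days". Limb 1 is a ceiling on a disease-activity score. Limb 2 is 30 days without escalation of the listed drugs and without hospitalization. The connector is AND/OR.

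The exclusion column of the same table removes candidates who "Have an initiation, a cessation or change of treatment of any chronic medications, dietary supplements, behavioral therapy, physical therapy etc". That clause also covers changes planned for the study period, but it gives no look-back period and does not mention hospitalization.

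Section 4.2.1 describes a full clinical assessment whose core measures include "disease activity (SELENA SLEDAI", along with serological status, without naming a visit. In section 4.7.1, "A screening phone call will be made to evaluate participant interest and eligibility", and lupus activity is taken from the SLAQ. The lupus-activity row of the section 4.6 schedule also names the SLAQ. Section 4.81 says of the SLAQ that "it will not detect abnormalities in laboratory findings among asymptomatic patients". Section 4.7.2 (baseline) mentions lupus disease activity without naming an instrument, and lists the SLAQ separately among the questionnaires.

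Section 9.1 adjusts the BFI model for baseline variables, with lupus disease activity as one example, only where they differ significantly at baseline. Section 4.3 names no stratification factor.

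**The concern.** An eligibility rule should give the same answer whoever applies it. This one does not. Two screeners acting in good faith, one reading AND and the other OR, would decide differently on the same patient with a score above 4 and a stable regimen. Under the literal reading, the definition does not deliver its own label, because a patient can be classed as inactive whatever the activity score.

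The score is also hard to trace. One limb depends on SELENA SLEDAI, but the schedule and the screening section point to a self-report tool that, by the protocol's own account, misses silent laboratory abnormalities. A screener working from the schedule alone would have no prompt to obtain the score before randomization.

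At stake are the description of the enrolled population and the comparability of arms of 18. If patients with a wide range of activity enter, nothing stratifies on activity, and adjustment depends on a baseline significance test.

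**Working it through.** The plan gives no figure on this point, so there is none to reproduce. The check is one of logic and of cross-reading.

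**Inputs.** From Table 2.0: the score ceiling of 4, the AND/OR connector, the 30-day window and the medication-change exclusion. From section 4.3: 72 participants, 18 per arm.

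**Step 1: truth table.** Limb 2 is met only with no escalation and no hospitalization in 30 days.

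| Score ≤ 4 | No escalation | No hospitalization | Either limb | Both limbs |
|---|---|---|---|---|
| yes | yes | yes | in | in |
| yes | yes | no | in | out |
| yes | no | yes | in | out |
| yes | no | no | in | out |
| no | yes | yes | **in** | **out** |
| no | yes | no | out | out |
| no | no | yes | out | out |
| no | no | no | out | out |

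Five of eight states qualify under the either-limb reading and one of eight under the both-limbs reading. The readings disagree in four states. The bold row is the one that conflicts with the label.

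**Step 2: cross with the medication-change exclusion.**

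- *If it covers the last 30 days*, the four states with an escalation are already out. Four remain. Under the either-limb reading only one of them is removed: score above 4 with a recent hospitalization.
- *If it covers only changes during the study*, the score limit also removes patients above 4 with a recent escalation. The either-limb reading then also admits patients at or below 4 who had a recent escalation.

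The documents do not say which applies.

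**Step 3: where the score would come from.** SELENA SLEDAI is named in Table 2.0 and section 4.2.1 only. The schedule and section 4.7.1 name the SLAQ. The unnamed activity measure in section 4.7.2 could be SELENA SLEDAI, since the SLAQ is listed there separately, but the text does not say so.

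**Step 4: illustration on assumed inputs.** Let *a* be the share of otherwise eligible candidates scoring above 4, and *q* the share of those who fail limb 2. Neither is in the documents. I take *a* from 20% to 50% and *q* from 0% to 10%.

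- Removed by the criterion under either-limb: *a* × *q*. Lowest 0%; highest 0.50 × 0.10 = 5%.
- Removed by the score limit under both-limbs: *a*, so 20% to 50%.
- Share above 4 among those who qualify under either-limb: *a*(1 − *q*) / (1 − *aq*). Lowest: 0.18 / 0.98 = 18.4%, or 13.2 of 72. Highest, with *a* = 50% and *q* = 0: 50%, or 36 of 72.

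These figures show how far the two readings can diverge. They do not estimate what this trial would enrol.

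**The case against.** The strongest reply is that AND/OR is ambiguous rather than wrong. A site may apply AND, and the score limit then binds. That is right, and it is why the point is put as two permitted populations.

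A reader might infer that the score limit excludes essentially nobody. The documents do not support that. It needs the either-limb reading and a medication-change exclusion that reaches back 30 days, and even then patients above 4 with a recent hospitalization are removed. Saying that the limit removes 0% of candidates who already meet limb 2 is true of any OR and measures nothing.

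A reader might also infer that limb 1 cannot be verified. That is too strong: section 4.2.1 says that SELENA SLEDAI is collected, and section 4.7.2 leaves room for it. What stands is a schedule that does not show it.

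It is tempting to add that active patients bring unrelated fatigue and more drug changes, and so more withdrawals under section 7.2.3. No section says so or gives a rate. One withdrawal is 1/18 = 5.6% of an arm, but nothing indicates how many this wording would cause. The title of one study in the reference list reports no correlation between lupus fatigue and disease activity.

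The aims speak only of fatigued people with lupus, so the inactive label rests on Table 2.0 alone. The glucocorticoid ceiling and the kidney-disease and anemia items narrow entry. None of them sets an activity limit.

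**Conclusion.** The point holds as a defect of definition and documentation. The wording admits two readings that disagree in four of eight states. Under the literal one, a patient above the score ceiling with no escalation or hospitalization in 30 days is classed as inactive. No scheduled visit names the score on which one limb rests.

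How many patients this affects cannot be stated, because the documents give no SELENA SLEDAI distribution. The range in the working depends wholly on assumed inputs. How little the score limit does under the literal reading depends on the look-back of the medication-change exclusion, which is unstated. Any effect on BFI, variance or withdrawals is likewise unquantified, and the conclusion does not rely on one.

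A reader might conclude that both limbs must be required. The documents do not settle that, and which eligibility rule is right is for the sponsor to say.

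**What to change.** 1. State one logical connector in Table 2.0 and make the inactive-disease label agree with it.
2. Reconcile Table 2.0 and section 4.2.1 with sections 4.6, 4.7.1 and 4.7.2, so that SELENA SLEDAI is shown at a named contact before randomization.
3. State the look-back period of the medication-change exclusion, so that its overlap with limb 2 is clear.
4. If either limb is meant to suffice, drop the inactive-disease label. Prespecify baseline disease activity as a covariate in the section 9.1 BFI model, in place of adjusting only when a baseline test is significant.

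The cost is a few words in Table 2.0, one schedule row and, for item 4, one sentence in section 9.1. There may be more screen failures, depending on the connector chosen.

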# 4.3 Randomization and Stratification.

Our randomization scheme will be created by our study statistician. Eligible patients will be randomized into one of four groups: once daily relaxing acupressure, once daily stimulating acupressure, once daily sham acupressure or usual care in a 1:1:1:1 ratio for a total of 72 participants with 18 randomized into each group.

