### 4.7.2 Randomization/Baseline- Participant Interaction #1 (Week 0, +/- 2 weeks)

Written informed consent will be obtained at the beginning of the study visit. Medication and health history, concomitant medications, lupus disease activity and urine pregnancy test results will be collected if applicable. Participants will complete BFI, SLAQ, PROMIS Fatigue Short Form 8 (PROMIS Fatigue 8), RAND SF-36, Pittsburg Sleep Quality Index (PSQI), the Brief Pain Inventory (BPI), Generalized Anxiety Disorder 7 (GAD7), The Satisfaction With Life Scale (SWLS), Fibromyalgia Survey Criteria (FM Survey Criteria), International Physical Activity Questionnaire (IPAQ) and The Positive and Negative Affect Schedule (PANAS). Participants will be instructed in how to perform their acupressure and told to start their acupressure on the following day. Participants will complete the Acupressure Fidelity test after the acupressure instruction has been completed. A study logbook will be dispensed, to document conduct of acupressure and the time of day. The post-treatment visit will be scheduled for exactly six weeks from the start day and the follow-up visit for four weeks post termination of treatment.

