### 4.8.10 Fibromyalgia Survey Criteria

The regional distribution of pain can help differentiate pain due to peripheral damage or inflammation (e.g., a few discrete regions) vs that seen in centrally-mediated syndromes such as fibromyalgia. A modified version of the Wolfe Regional Pain Scale will be used that queries for the existence of pain in 19 bodily regions, using a checklist allowing for efficient scoring, along with the Wolfe Symptom Inventory (SI); a "fibromyalgianess" score can thus be calculated. The presence or absence of comorbid fibromyalgia (thought to occur in at least ~20% of SLE patients) is the largest predictor of pain, fatigue, and function in SLE; across various rheumatic

diseases, SI scores are associated with greater severity of disease (including mortality) and sociodemographic disadvantage.

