### 9.0 STATISTICAL METHODS

Baseline sociodemographic and clinical characteristics will be analyzed by treatment groups, using means and standard deviations (SD), counts and percentages as appropriate. Comparisons between groups on baseline characteristics will be tested using an independent sample t-test for continuous measures or Pearson's Chi-square, for categorical variables. In all analyses, a p-value of  $\leq$  0.05 was considered statistically significant. All tests will be two-sided.

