## 9.1 Primary and Secondary Aims

To investigate the change through time both within and between groups for fatigue (BFI), we will use linear mixed models (LMM). An advantage of LMM is that it acts as essentially an intent-to-treat (ITT) analysis as it uses all available data at each time point. For each LMM, a random subject intercept will be included to account for subject clustering; visit, group, and the interaction term (visit by group), will also be included as fixed effects. The models for BFI will be controlled for the fixed effects of any baseline variable such as age or lupus disease activity that is significantly different at baseline. Normality of the residuals derived from the LMM will be assessed using the Shapiro–Wilk test and q-q plots. For non-normal results a Box-Cox transformation will be utilized. The same methods will be employed to investigate secondary outcomes of interest pain (BPI severity sub-scale), sleep (PSQI global score) and quality of life (RAND SF-36).

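### Section 9.1 adjusts the BFI models for fibromyalgia only if a baseline test happens to be significant, although the protocol ranks it the top predictor of fatigue and section 4.3 names no stratification factor

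*Combined protocol and SAP*

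**What the plan says.** **Allocation.** The heading is "4.3 Randomization and Stratification". The text beneath it says "Our randomization scheme will be created by our study statistician" and that patients are allocated "in a 1:1:1:1 ratio for a total of 72 participants with 18 randomized into each group". It names no stratification factor, block size or minimisation rule, and no other section supplies one.

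**Fibromyalgia.** Section 4.8.10 describes comorbid fibromyalgia as "thought to occur in at least ~20% of SLE patients" and says that it "is the largest predictor of pain, fatigue, and function in SLE". The schedule in section 4.6 and the visit description in section 4.7.2 place the survey at the baseline interaction, where randomisation also takes place.

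**Model.** Section 9.1 fits a linear mixed model with visit, group, visit by group and a random subject intercept. The only covariate rule is to control for "any baseline variable such as age or lupus disease activity that is significantly different at baseline". Section 9.0 sets the baseline test as an "independent sample t-test for continuous measures or Pearson's Chi-square, for categorical variables", two-sided at 0.05. It does not say how four arms are to be compared. Fibromyalgia is not named as a covariate.

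**The concern.** The protocol identifies one variable as the strongest predictor of its primary outcome and measures it before treatment starts. It then uses that variable neither in allocation nor, by default, in the analysis. Whether it enters the model depends on a significance test with low power in arms of 18. That rule selects covariates by chance imbalance rather than by prognostic value, so the final model cannot be known in advance.

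Two things are at stake. One is the comparison of BFI level between arms, the group test for which section 9.2 claims power above 0.80. The other is any part of the visit-by-group contrast that depends on fibromyalgia changing the course of fatigue.

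**Working it through.** **Inputs from the documents.** Four arms of 18, 72 in total (section 4.3). Fibromyalgia in at least about 20% (section 4.8.10). Baseline tests at 0.05 (section 9.0). Planned week 6 BFI means of 4, 3 and 2, hence steps of 1 point (section 9.2). BFI recorded at baseline and weeks 2, 6 and 10 (section 4.6).

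**Inputs assumed.** A fibromyalgia effect of 1 to 2 BFI points, and a share of variance explained (R²) of 10 to 30%. The documents give neither.

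**Step 1: the plan's arm size.** 15 completers with one in six lost: 15 / (1 − 1/6) = 18 per arm, and 4 × 18 = 72. This reproduces section 9.2.

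**Step 2: how often arms differ.** 20% of 72 is 14.4, so take 14 positives and allocate them at random to four arms of 18 (multivariate hypergeometric simulation).

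| Gap | Some two arms | One named pair |
|---|---|---|
| 3 or more patients | 75% | about 29% |
| 4 or more patients | 46% | 14% |

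Treating each arm as Binomial(18, 0.20) gives 71% and 45% for some two arms, and 29% and 14% for a named pair. At a prevalence of 30 to 50% (an assumption; 20% is stated as a floor), the chance that some two arms differ by 4 or more is 57 to 65%.

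**Step 3: would the baseline test trigger adjustment?** Take 6/18 against 2/18. The pooled proportion is 8/36 = 0.222. The standard error is √(0.222 × 0.778 × 2/18) = 0.139. Then z = (4/18)/0.139 = 1.60 and p = 0.11, so there is no adjustment. A split of 4/18 against 0/18 would be flagged: chi-square = 36 × (4 × 18)² / (18 × 18 × 4 × 32) = 4.5, p = 0.03.

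Over all allocations with a gap of 4 or more:
- the four-arm chi-square is significant in about 8%, so about 92% are missed;
- with pairwise tests, the widest pair is significant in about 44%, so about 56% are missed.

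For gaps of 5 or more, pairwise testing flags about 89%.

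**Step 4: effect on the two contrasts.** Let p₁ and p₂ be the proportions with fibromyalgia in two arms.
- *Stable effect β on level.* Each arm's mean shifts by β × p at every visit. The difference in level shifts by β(p₁ − p₂) = (1 to 2) × 4/18 = 0.22 to 0.44 points. The difference in change shifts by β(p₁ − p₂) − β(p₁ − p₂) = 0 with complete data and baseline BFI as an outcome visit.
- *Effect γ on change.* The difference in change shifts by γ(p₁ − p₂). With γ = 1 point (assumed for illustration), that is 0.22 points.

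I fitted the section 9.1 model to one simulated complete data set, split 6, 2, 3 and 3, with total variance 4 and intra-class correlation 0.5 (assumed). Adding a constant 2-point fibromyalgia effect left the visit-by-group estimate and its standard error unchanged, with or without a fibromyalgia main effect. Adding a 1-point effect on change moved the estimate by 0.22. A fibromyalgia main effect did not correct this; a fibromyalgia-by-visit term did.

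**Step 5: precision.** For a comparison of level, adjustment multiplies the standard error by about √(1 − R²): √0.90 = 0.949 to √0.70 = 0.837, a saving of 5 to 16%. For the change contrast there is no saving if fibromyalgia does not affect change.

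The cost of the extra term for the 6 against 2 split is as follows. The within-arm sum of squares of the indicator is 6×12/18 + 2×16/18 + 2 × (3×15/18) = 10.78. The variance factor goes from 2/18 = 0.1111 to 0.1111 + (4/18)²/10.78 = 0.1157. Since √(0.1157/0.1111) = 1.02, the standard error is about 2% wider.

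**The case against.** The strongest reply is that the analysis targets change over time. With baseline BFI as an outcome visit, a steady difference in fatigue between patients with and without fibromyalgia drops out of the visit-by-group contrast. This is correct, and it limits the point: the 0.22 to 0.44 shift and the 5 to 16% precision gain do not apply to that contrast. It does not protect the group test, nor the interaction if fibromyalgia alters the course of fatigue or the response to treatment.

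Second, simple randomisation is valid, chance imbalance is already allowed for in the test's error rate, and this is a pilot whose first aim is feasibility. All true. No bias on average is alleged. Even so, section 2.0 states superiority hypotheses on the BFI and section 9.2 powers them, and small arms are where conditional imbalance matters most.

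Third, section 9.1 does not exclude fibromyalgia, and section 9.0 can be read as pairwise testing, or as a t-test on the survey score. Under pairwise chi-square tests most gaps of 5 or more would be caught. That stands, but the plan does not say which test applies, and more than half of gaps of 4 or more are missed even so.

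Fourth, the prevalence and the ranking as top predictor describe SLE patients in general, whereas this trial enrols only those with BFI of 4 or more and excludes other recognised causes of fatigue. Prevalence and predictive strength in that group are unknown, so the sizes remain conditional.

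**Conclusion.** The point holds as a gap in the analysis plan. A covariate that the protocol itself ranks first is left to a test that would miss about 56 to 92% of gaps of 4 or more patients. Such a gap somewhere among the four arms has a probability of about 46%, given 14 of 72 positive. The possible shift is 0.22 to 0.44 points on between-arm BFI level, against planned steps of 1 point, assuming a 1 to 2 point effect. For the visit-by-group contrast the exposure is limited to a fibromyalgia effect on change, whose size the documents do not give.

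A reader might infer three stronger things that the documents do not support:
- *That a 4-patient imbalance is likely in a planned comparison.* The 46% is for the widest of six pairs; for a named pair it is 14%.
- *That the change contrast is shifted by 0.22 to 0.44 points, or loses 5 to 16% in precision.* A stable effect cancels there.
- *That the allocation is invalid, or that a planned stratification was dropped.* The documents show only a heading with no factor beneath it.

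This is worth changing because the remedy is nearly free. It is not a fatal flaw.

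**What to change.** In section 9.1, replace the significance-triggered rule with a prespecified one: every BFI model includes baseline fibromyalgia status (or the baseline survey score; choose one in advance) and its interaction with visit as fixed effects, regardless of baseline p-values. The interaction is needed because a main effect alone does nothing for the change contrast. Name any other covariates, such as age or lupus activity, in advance on the same footing, and keep the baseline table descriptive.

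The cost is a few degrees of freedom (one for the main effect and up to three for the interaction over four BFI visits). If fibromyalgia does not affect change, the standard error on the change contrast is also about 2% wider at a 6 against 2 split.

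Optionally, if allocation has not started, score the survey before randomising at the baseline interaction and use permuted blocks within fibromyalgia yes/no. Blocks of 4 hold the fibromyalgia gap between any two arms to 1 patient, and blocks of 8 to 2. The price is two lists instead of one, and arm sizes that may differ from 18 by one or two. If allocation stays as it is, remove the word Stratification from the section 4.3 heading.
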